8.2.3 Cohort B – End of Stage 1 – Efficacy Analysis

In cohort B after 1 response has been confirmed, a subgroup of the DRC will meet to confirm continuation to Stage 2 and evaluation of 16 further patients. An interim analysis (Stage 1) will be conducted after 13 evaluable patients have at least 1 on-treatment scan. This data will be reviewed by the DRC.

Appropriate representatives of the Sponsor and the coordinating personnel may also attend and minute DRC meetings. Recommendations of the DRC will be documented and sent to the sites. Further details on the composition of the DRC, as well as the process for data review, issue of recommendations and decision making, are described in a separate DRC charter for this study.

8.2.4 Cohort C – End of Stage 1 – Efficacy Analysis

In cohort C after 1 response has been confirmed, a subgroup of the DRC will meet to confirm continuation to Stage 2 and evaluation of 16 further patients. An interim analysis (Stage 1) will be conducted after 13 evaluable patients have at least 1 on-treatment scan. This data will be reviewed by the DRC.

Appropriate representatives of the Sponsor and the coordinating personnel may also attend and minute DRC meetings. Recommendations of the DRC will be documented and sent to the sites. Further details on the composition of the DRC, as well as the process for data review, issue of recommendations and decision making, are described in a separate DRC charter for this study.

8.3 Statistical Analysis Plan

Detailed statistical analysis information will be provided separately in the Statistical Analysis Plan (SAP). The SAP will detail all data handling rules e.g., full definition of patient populations for analysis, including the management of missing values and the handling of data for patients lost to follow-up or missing other important information. The SAP will also outline protocol deviation criteria. Any deviations to the planned analyses specified or populations defined within the SAP will be justified in writing and presented within the final clinical study report. It will also describe the rules the handling of missing data points for the primary, secondary and exploratory endpoints.

The SAP will fully describe the efficacy analyses and descriptive summaries that will be undertaken for both the interim (Stage 1 and Stage 2) analyses for each cohort, as well as the final

BerGenBio ASA

[name]

[name]

Norway

analyses for all cohorts. All efficacy endpoints (ORR, DoR, PFS, DCR, and OS) will be summarized and described for both the interims and final analyses for all cohorts ([Section 8.12.2](#)). Summaries of ORR by PD-L1 and Axl expression will be provided only for the final analyses.

The clinical database lock for the cohort A final analysis will occur after the final patient in that cohort has been followed-up for at least 24 months for disease assessment and after all data are reconciled (i.e., “cleaned”) for all patients who participate in this cohort.

The clinical database lock for the cohort B final analysis will occur after the final patient in that cohort has been followed-up for at least 24 months for disease assessment and after all data are reconciled (i.e., “cleaned”) for all patients who participate in this cohort.

The clinical database lock for the cohort C final analysis will occur after the final patient in that cohort has been followed-up for at least 24 months for disease assessment and after all data are reconciled (i.e., “cleaned”) for all patients who participate in this cohort.

A single clinical study report (CSR) will be generated. The SAP will be finalized and signed before the database lock. An addendum (or addenda) to report SAEs from patients remaining on treatment at the time of Last Patient Last Visit ([Section 8.6](#)) until study closure will be written.

The main data analyses intended for this trial are briefly described in this section. The SAP will provide full details of all planned data analyses for the primary, secondary and exploratory objectives of the study.

8.4 Population

The efficacy objectives will include all evaluable patients (EE) that have received at least one dose of bemcentinib and/or pembrolizumab and have measurable disease at entry according to the Investigator Site Assessment and who meets the inclusion/exclusion criteria and have at least 1 on-treatment scan.

For all safety objectives, the safety set, consisting of all patients (ES) who have received at least one dose of bemcentinib and/or pembrolizumab, will be used.

For some objectives (pharmacokinetics and biomarker) a subgroup of patients of the safety set with respective baseline and post-baseline measurements will be used.

Patients who signed a consent form and were screened but did not receive any treatment will be listed if they reported an adverse event in the time after consent and before treatment allocation (see [Section 7.1](#)). All AEs that occur after the consent form is signed but before treatment allocation must be reported if they cause the patient to be excluded from the trial, or are result of protocol-specific intervention, including but not limited to, washout or discontinuation of usual therapy, diet, placebo treatment or a procedure ([Section 7.1](#))

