2 STUDY OBJECTIVES AND ENDPOINTS

The objective of this study is to assess the anti-tumor activity of the combination treatment of bemcentinib and pembrolizumab in patients with previously treated, advanced adenocarcinoma of the lung.

The study will enroll three cohorts of patients with previously treated advanced adenocarcinoma of the lung: Cohort A will consist of patients who received a maximum of one prior line of platinum-containing chemotherapy and no prior immunotherapy of any kind. Cohort B will consist of patients with a maximum of one prior line of an anti-PD-(L)1 therapy (monotherapy). Cohort C will consist of patients who received a maximum of one prior line of therapy with an anti-PD-(L)1 therapy in combination with a platinum-containing chemotherapy.

Objective	Endpoint (Assessment)
Primary:	
• To assess the anti-tumor activity of bemcentinib and pembrolizumab when given in combination.	• Objective Response Rate (complete response and partial response).
Secondary:	
• To assess the safety of bemcentinib and pembrolizumab when given in combination.	• The number and frequency of adverse events; assessment of safety laboratory parameters, vital signs, and ECGs.
• To further assess the anti-tumor activity of the combination of bemcentinib and pembrolizumab.	• To include Disease Control Rate, Duration of Response, Progression-free Survival, median Overall Survival, and 12-month Overall Survival.
• To evaluate the pharmacokinetic profile of bemcentinib when given with pembrolizumab.	• Assessment of pharmacokinetic variables including C_{max} , AUC, and $t_{1/2}$
Exploratory:	
• To assess relevant biomarkers.	• To assess PD-L1 and Axl expression in patients with adenocarcinoma of the lung.
	• To assess any correlation or association between expression level of PD-L1 and Axl and anti-tumor outcomes such as ORR.
	• Assessment of relevant biomarkers in tumor and blood which support immune modulation and Axl signaling.
	• Developing a radiomic signature as a response prognostic biomarker.

BerGenBio ASA
[name]
[name]
Norway

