3.5 Definition of Evaluable Patient, Acceptable Compliance, and Replacement of Patients

Evaluable for safety (ES): An evaluable patient will have received at least one combination dose.

Evaluable for efficacy (EE): An evaluable for safety patient who has at least one on-treatment scan per protocol schedule.

Patients will be replaced if they are considered to be non-evaluable for efficacy.

Patients who have failed screening (usually because they have failed one or more of the inclusion or exclusion criteria) will not receive study treatment and are not considered evaluable.

Treatment non-compliance for this study will be defined as follows:

- For bemcentinib: missing more than 7 doses in any 21-day period (other than a dose delay for toxicity management ([Section 6.6.1](#)))
- For pembrolizumab: Dosing interruptions are permitted in the case of medical / surgical events or logistical reasons not related to study therapy (for example, elective surgery, unrelated medical events, patient vacation etc). Patients should be placed back on study therapy within 3 weeks of the scheduled interruption. The reason for the interruption should be documented in the patient's study notes.

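### PFS, median OS and 12-month OS fall by default to patients who reached an on-treatment scan, so earlier deaths are left out and the estimates are biased upward

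*Combined protocol and SAP*

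**What the plan says.** Section 8.4 sets the population: "The efficacy objectives will include all evaluable patients (EE", and it further requires that they "have measurable disease at entry according to the Investigator Site Assessment and who meets the inclusion/exclusion criteria and have at least 1 on-treatment scan". Section 3.5, like the synopsis, defines EE as "An evaluable for safety patient who has at least one on-treatment scan per protocol schedule" and adds: "Patients will be replaced if they are considered to be non-evaluable for efficacy".

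PFS and OS count as efficacy endpoints. Section 2 lists the measures under the further anti-tumor activity objective: "To include Disease Control Rate, Duration of Response, Progression-free Survival, median Overall Survival, and 12-month Overall Survival". Section 8.3 says: "All efficacy endpoints (ORR, DoR, PFS, DCR, and OS) will be summarized and described". Section 8.12.2.3 defines both endpoints, with PFS timed from first dose and OS from enrolment, and names no population. Section 8.6 ties the final analysis to EE patients. Section 8.3 leaves the full population definitions to a separate SAP that is not among the documents.

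The definitions also disagree with one another:

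| Set | Synopsis and Section 3.5 | Section 8.4 |
|---|---|---|
| Evaluable for safety (ES) | "An evaluable patient will have received at least one combination dose" | "consisting of all patients (ES) who have received at least one dose of bemcentinib and/or pembrolizumab" |
| EE | ES plus a scan on the protocol schedule | At least one dose of either drug, any on-treatment scan, eligibility and measurable disease |

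**The concern.** Membership of EE is decided by something that happens about nine weeks after the PFS clock has started. A treated patient who dies in week 6 without a scan has had both a PFS event and an OS event under the protocol's own definitions, yet cannot enter the analysis. Everyone who remains is known to have lived long enough to be scanned. This is guarantee-time (immortal-time) bias.

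The trial has no control arm, so median PFS, median OS and 12-month OS will be read on their own as describing the patients treated. Under EE they describe patients who survived to a scan. The documents name no outside comparator for PFS or OS. The one pembrolizumab reference they give, for ORR, counts patients who received at least one dose. ORR and DCR share the EE denominator, but that is a separate question.

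**Working it through.** The plan states no planning figure for PFS or OS, so there is nothing of its own to reproduce. The check has three parts.

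**1. Is an early death really excluded?**
- First on-treatment scan: nine weeks ± 7 days after first treatment (Sections 5.3.10 and 8.5), which is day 56 to 70 and is scheduled as week 10 in Section 5.1.1.
- A patient who dies before any on-treatment scan fails EE under both Section 3.5 and Section 8.4.
- Nothing brings the patient back. The loss-to-follow-up summary in Section 8.12.2.3 is for patients whose status is unknown. The Kaplan–Meier sentence in Section 8.11 concerns evaluable patients who respond after a later therapy.
- The data exist: survival status is checked every 12 weeks until death or study end (synopsis; also Section 5).

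**2. Size of the effect.** Let S(t) be survival in all treated patients and q the share who die before the scan. For any t after the scan, S_EE(t) = S(t) / (1 − q). The documents give no q, so it is varied as an assumption. With S(12 months) = 33%, the one-year figure in Section 1.1:

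| q | EE 12-month OS | Bias (points) |
|---|---|---|
| 2% | 0.33/0.98 = 33.7% | +0.7 |
| 5% | 0.33/0.95 = 34.7% | +1.7 |
| 10% | 0.33/0.90 = 36.7% | +3.7 |
| 15% | 0.33/0.85 = 38.8% | +5.8 |

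To see what q might be, Weibull curves were drawn through the Section 1.1 figures (median 8 to 10 months, 33% alive at one year), with months of 30.44 days. The EE median solves S(t) = 0.5 × S(t0), where t0 is the scan day. Ranges are for t0 from day 56 to day 70:

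| True median (shape) | Dead before scan | 12-month OS (points) | Median OS (months) |
|---|---|---|---|
| 8 months (1.16) | 11.9% to 15.1% | +4.4 to +5.9 | +1.24 to +1.61 |
| 9 months (1.63) | 5.1% to 7.2% | +1.8 to +2.6 | +0.41 to +0.58 |
| 10 months (2.58) | 0.9% to 1.6% | +0.3 to +0.5 | +0.05 to +0.09 |

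A constant hazard with the same medians gives +5.9 to +7.8 points and +1.8 to +2.3 months. However, it implies 35% to 44% alive at one year, which does not fit the 33%.

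PFS follows the same identity. Assuming 6-month PFS of 20% with q = 1.2%, the shift is 0.20/0.988 − 0.20 = +0.2 points. With 50% and q = 13.5%, it is 0.50/0.865 − 0.50 = +7.8 points.

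In patient counts:
- 10 of 29 EE patients alive at 12 months is 34.5%. Adding back 1, 3 or 5 early deaths gives 10/30 = 33.3%, 10/32 = 31.3% or 10/34 = 29.4%.
- 16 of 48 is 33.3%. Adding back the same numbers gives 16/49 = 32.7%, 16/51 = 31.4% or 16/53 = 30.2%.

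**3. Patients who leave alive without a scan.** Here the direction is not fixed. Suppose 10% leave this way, their later follow-up is discarded, and overall 12-month OS is 33%. The EE estimate is (0.33 − 0.1 × s)/0.9, where s is their own 12-month OS. For s = 11%, 33% or 50%, the shift is +2.4, 0.0 or −1.9 points.

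**Sampling error for scale.** The 95% half-width is 1.96 × √(0.33 × 0.67/n), which is 17.1 points at n = 29 and 13.3 at n = 48.

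**The case against.** The best counter-argument is that the governing document is missing. Section 8.3 defers population definitions to the SAP. ORR and DCR are given explicit EE denominators in Sections 8.11 and 8.12.2.2, while Section 8.12.2.3 is silent, which could mean PFS and OS were left for the SAP to settle. That is possible, and it is why the point is made about the default. As the text stands, though, Section 8.4 covers the efficacy objectives without exception and Section 8.6 points the same way.

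Second, Section 8.4 accepts any on-treatment scan, and Section 5.3.10 allows unscheduled imaging. A deteriorating patient scanned at week 5 who dies at week 7 would be EE under that wording. This lowers q, so for each curve the figures above lean high. It does not help under the synopsis and Section 3.5, which require a scan on schedule.

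Third, the Section 1.1 survival runs from Stage IV diagnosis, not from this trial's baseline. ECOG 0–1, life expectancy of at least 3 months and, in cohorts B and C, prior disease control should make early deaths rarer. The fitted shapes rest on very little, and the 6-month PFS range has no source in the documents. This stands: the curves are illustrations, and only the identity is firm.

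Fourth, PFS and OS are secondary and descriptive, with no hypothesis test, and sampling error exceeds the bias. That limits the consequence without removing it, because the planned 95% interval will not reflect a systematic shift. Replacement as such adds no bias; exclusion does.

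**Conclusion.** The concern holds. Followed as written, the plan removes treated patients who die before an on-treatment scan from the PFS and OS analyses, although those deaths are events on clocks that have already started. For those deaths the bias is upward, and it is zero only if there are none. The net direction across all exclusions is less certain, because patients who leave alive, or who fail the eligibility or measurable-disease conditions, could move the estimate either way.

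The size depends on an early-death rate that the documents do not give. On the illustrative Weibull curves it runs from +0.3 to +5.9 points on 12-month OS and from +0.05 to +1.6 months on median OS. This is a fault in a secondary analysis that should be corrected; the ORR decision rules are not part of this finding. The conclusion assumes that the unseen SAP does not name a different population for PFS and OS.

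**What to change.** - In Sections 8.4 and 8.12.2.3, make the main analysis of PFS, median OS and 12-month OS all patients who received at least one dose of either drug, with deaths before the first scan counted as events. Describe the set in words and not as ES until the ES definition is settled. Carry the same wording into the SAP.
- Keep EE, or a week-10 landmark, as a sensitivity analysis.
- Report for each cohort how many treated patients are outside EE and why.
- Reconcile the ES definition (synopsis and Section 3.5 against Section 8.4) and the EE definition (synopsis and Section 3.5 against Section 8.4).

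The cost is protocol and SAP wording. Dosing, deaths and survival status are already collected for treated patients. The price is likely to be slightly less favorable PFS and OS estimates.

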- ~ Bemcentinib dosing [REDACTED] (daily oral dosing 21-day cycle)
- ~ PK sampling - bemcentinib (pre-dose)
- ~ PK sampling for storage – pembrolizumab (pre-dose)
- ~ Adverse events
- ~ Concomitant medication

Cycle 1, Day 8

- ~ Vital signs
- ~ Physical examination
- ~ Clinical chemistry
- ~ Hematology
- ~ Coagulation
- ~ Urinalysis
- ~ ECG (triplicate test; pre-dose)
- ~ Biomarkers
- ~ Bemcentinib dosing [REDACTED] (daily oral dosing 21-day cycle)
- ~ PK sampling - bemcentinib (pre-dose)
- ~ PK sampling for storage – pembrolizumab (pre-dose)
- ~ Adverse events
- ~ Concomitant medication

Cycle 1, Day 15

- ~ Vital signs
- ~ Physical examination
- ~ Clinical chemistry
- ~ Hematology
- ~ Coagulation
- ~ Urinalysis
- ~ ECG (triplicate test; pre-dose)
- ~ Bemcentinib dosing [REDACTED] (daily oral dosing 21-day cycle)

BerGenBio ASA
[name]
[name]
Norway

- ~ PK sampling bemcentinib (pre-dose)
- ~ PK sampling for storage – pembrolizumab (pre-dose)
- ~ Adverse events
- ~ Concomitant medication

Cycle 2- Cycle 3 Day 8, Day 15 (every week)

- ~ Clinical chemistry
- ~ Adverse events
- ~ Concomitant medication

Cycle 2-35 (every 3 weeks), Day 1

- ~ Pregnancy test (if applicable)
- ~ ECOG PS
- ~ Vital signs
- ~ Physical examination
- ~ Clinical chemistry
- ~ Hematology
- ~ Coagulation
- ~ Urinalysis (performed on Cycle 2 Day 1 only)
- ~ Thyroid function tests (performed after every 2 cycles i.e., Cycles 3, 5, 7, 9, 11, 13, 15, 17 in Year 1 and then Cycles 19, 21, 23, 25, 27, 29, 31, 33, 35 in Year 2)
- ~ ECG (triplicate test; pre-dose)
- ~ Echocardiogram (or MUGA) (performed at Cycles 9, 17, 25 and 33)
- ~ Tumor assessment scans (performed at cycles 4, 7, 10, 13, 16, 20, 24, 28, 32 or weeks 10, 19, 28, 37, 46, 58, 70, 82, 94, 106, and then every 12 weeks until progression)
- ~ Disease assessment (performed at cycles 4, 7, 10, 13, 16, 20, 24, 28, 32 or weeks 10, 19, 28, 37, 46, 58, 70, 82, 94, 106, and then every 12 weeks until progression)
- ~ Tumor biopsy (up to 2 optional on treatment biopsies)
- ~ Biomarkers (performed only at Cycles 2-9)
- ~ Pembrolizumab dosing 200 mg fixed dose (infusion)
- ~ Bemcentinib dosing [REDACTED] (daily oral dosing 21-day cycle)
- ~ PK sampling bemcentinib (pre-dose cycles 2 and 3 only)
- ~ PK sampling - pembrolizumab (pre-dose cycles 2 and 3 only)
- ~ Adverse events
- ~ Concomitant medication

Cycle 36 – 71 (every 3 weeks), Day 1

- ~ Pregnancy test (if applicable)
- ~ ECOG PS
- ~ Vital signs

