8.12.2.3 Progression free survival and overall survival

Kaplan Meier plots of the time to progression and death will be presented, along with the median progression free survival (PFS), median overall survival (mOS), and overall survival (OS), as well as the estimated survival at 12 months. Descriptive statistics will be used as required, including 95% CI.

PFS is measured from the date of the 1st dose of the 1st cycle until the date of progression (the date on which the progression is initially observed) or the date of death (whichever is earlier). A sensitivity summary of PFS using the first date that a progression is considered (irrespective of whether confirmed) will additionally be conducted. Patients who have not progressed or died before the date of data cut-off (last patient, last visit) will be censored at their last clinical evaluation.

BerGenBio ASA
[name]
[name]
Norway

OS is defined as the time from the date of enrolment until the date of death (from any cause and irrespective of any subsequent anti-cancer treatment given). Patients who remain known to be alive at the date of data cut-off (LPLV) will be censored at their date last known to be alive. The estimated survival at 12 months will be read from the Kaplan Meier OS curve. Patients who are lost to follow-up will be censored at the point last known to be alive; however, if $\geq 2\%$ of patients are in this category, a sensitivity summary will be produced to illustrate the overall survival assuming the patient died at the date last known in the trial. If possible, the date of death may be recovered from publicly available sources such as death registries.

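### As written, PFS, median OS and 12-month OS are restricted to patients with an on-treatment scan, so deaths before that scan leave the curves and survival is biased upward

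*Combined protocol and SAP*

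**What the plan says.** Section 8.4 sets the population for efficacy: "The efficacy objectives will include all evaluable patients (EE"). It limits that set to dosed patients with measurable disease "who meets the inclusion/exclusion criteria and have at least 1 on-treatment scan". Section 3.5 defines the same set slightly differently, as "An evaluable for safety patient who has at least one on-treatment scan per protocol schedule", and adds: "Patients will be replaced if they are considered to be non-evaluable for efficacy".

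Section 8.3 places survival under efficacy: "All efficacy endpoints (ORR, DoR, PFS, DCR, and OS) will be summarized". Section 8.6 defines study completion, and the data for the final analysis, in terms of EE patients. Section 8.4 also defines a safety set of all patients given at least one dose of either drug, but assigns it to the safety objectives.

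Section 5.1 schedules on-treatment scans at "weeks 10, 19, 28, 37, 46, 58, 70, 82, 94, 106", and footnote 7 to the assessment tables allows ± 7 days. Section 8.12.2.3 starts PFS at the first dose of cycle 1 and OS at enrolment, and says: "The estimated survival at 12 months will be read from the Kaplan Meier OS curve". It names no analysis population, landmark or delayed entry for either endpoint.

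**The concern.** A response rate needs a scan; a survival time does not. Every dosed patient has a survival time, and survival status is followed every 12 weeks until death or study end (synopsis, study procedures), including in patients who stop treatment but stay in the study (Section 3.3). Requiring a scan for entry to the survival curves selects patients on something that happens after the clock has started. Those who die first are taken out and replaced by patients who lived long enough to be scanned.

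PFS, median OS and 12-month OS are named secondary endpoints of a single-arm trial, so readers will judge them against outside experience. Curves that omit the earliest deaths would look better than survival counted in all treated patients. PFS may also inform the cohort A Stage 1 recommendation, where Section 8.2.2 lets the DRC consider it if available.

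**Working it through.** The plan states no expected PFS or OS and no early-death rate, so there is no figure of its own to reproduce. The check has three parts.

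**1. Which set do PFS and OS use?** Section 8.4 gives efficacy objectives to EE, Section 8.3 lists PFS and OS as efficacy, and Section 8.6 ties the final analysis to EE. Nothing in the document commits to an all-treated survival analysis. The two sensitivity summaries in Section 8.12.2.3 (first unconfirmed progression for PFS; loss to follow-up for OS) do not bring back patients without a scan.

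**2. How long is the guaranteed survival?** Week 10 starts 9 weeks after first dose (day 64). With ± 7 days, the first scheduled scan falls between day 57 and day 71. This applies under the Section 3.5 wording. Section 8.4 does not mention the schedule, so under its wording an earlier unscheduled scan could qualify a patient, and the guaranteed period would end at that scan.

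**3. How large could the effect be?**

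*Without a survival model.* Let d be the share of dosed patients who die before a qualifying scan, with no other exclusions. After the scan, S_EE(t) = S_all(t) / (1 − d). Assume a true 12-month OS of 40%:

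- d = 5%: 0.40 / 0.95 = 42.1%
- d = 10%: 0.40 / 0.90 = 44.4%

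The direction is upward whenever d is above zero.

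*Exponential illustration.* Assume a median m of 9 months, the middle of the 8 to 10 months that Section 1.1 quotes for Stage IV disease, and a cut at day 57: t0 = 57 / 30.44 = 1.87 months.

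- Share surviving to t0: 2^(−1.87/9) = 0.866, so 13.4% are removed.
- 12-month OS, all dosed: 2^(−12/9) = 39.7%.
- 12-month OS, given survival to t0: 0.397 / 0.866 = 45.8%, about 6 points higher.
- Median: 9 + 1.87 = 10.87 months, about 1.9 months higher.

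With m = 8 or 10 months, 12-month OS goes from 35.4% to 41.6%, or from 43.5% to 49.6%. With the cut at 9 weeks (2.07 months), the restricted values are 42.3% and 50.2%, and the median rises by about 2.1 months.

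*Lower early hazard.* Patients are selected for a life expectancy of at least 3 months, so let the hazard before t0 be a fraction f of the later hazard (m = 9). The restricted curve still gives 45.8% at 12 months. The all-dosed value is 0.458 × 2^(−f × 1.87/9), and the median shift is f × 1.87.

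| f | Removed | 12-month OS, all dosed | Rise in 12-month OS | Rise in median |
|---|---|---|---|---|
| 1 | 13.4% | 39.7% | about 6 points | 1.9 months |
| 1/2 | 7.0% | 42.6% | 3.2 points | 0.9 months |
| 1/4 | 3.5% | 44.2% | 1.6 points | 0.5 months |

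*PFS.* If only pre-scan deaths are lost and PFS is exponential with median m, the restricted median is m × (1 − log2(1 − d)). With an assumed median of 4 months, d = 5% gives 4.3 months and d = 10% gives 4.6 months.

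**The case against.** **The restriction is inferred.** Sections 8.11 and 8.12.2.2 name EE as the denominator for ORR and DCR, while Section 8.12.2.3 names no set for PFS or OS. Section 8.3 leaves the full population definitions to a separate SAP. This stands as a reason for conditional wording: the authors may have meant all dosed patients. It does not remove the point, because Section 8.4 sets the default for every efficacy objective and nothing in the document departs from it.

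**A reader might infer that nobody in the survival analysis can have died before day 57.** The documents do not support that absolute. It needs the schedule condition of Section 3.5, which Section 8.4 omits, and Section 5.3.10 expects scans when clinically indicated. A patient scanned early for symptoms who then dies could count as evaluable under Section 8.4. The looser wording shortens the immortal time but does not abolish it.

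**A reader might take 6 points and 1.9 months as the expected bias.** They are not. The Section 1.1 medians are background figures, and its accompanying 33% alive at one year is counted from diagnosis; that 33% is also below the 35.4% to 43.5% the exponential model gives. This trial enrols ECOG 0–1 patients expected to live at least 3 months, and cohorts B and C must have had disease control on prior anti-PD-(L)1 therapy. The reduced-hazard rows may be nearer the truth.

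**A reader might conclude that the trial's decisions are compromised.** They are not: the Stage 1 futility rules and the final rejection rules use ORR alone. The losses are also not invisible, since dosed patients stay in the safety set and reasons for stopping treatment are summarised (Section 8.10).

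**Conclusion.** The point holds in conditional form. Read together, Sections 8.3, 8.4 and 8.6 restrict PFS, median OS and 12-month OS to patients with an on-treatment scan, while both clocks start before that scan. Removing pre-scan deaths biases the Kaplan-Meier estimates upward. That direction needs no survival model, only that at least one such death occurs. Patients who stop alive without a scan are lost as well; the effect of losing them depends on their prognosis, and it adds to the bias if they stopped because they were deteriorating.

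The size is unknown because the early-death rate is not given. The illustrations run from about 1.6 points in 12-month OS and 0.5 months in the median (a quarter of the assumed early hazard) to about 6 points and 1.9 months (the full hazard), all with a 9-month exponential median and a cut at about 8 weeks. For scale, Section 8.12.2.3 asks for an OS sensitivity summary once 2% of patients are lost to follow-up; even the quarter-hazard case removes 3.5% as known deaths with no such summary.

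This should be fixed, but it is not critical: the endpoints are secondary and descriptive, with no hypothesis or sample size attached.

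**What to change.** State in Sections 8.4 and 8.12.2.3, and carry into the SAP before database lock, that PFS, OS and 12-month OS are analysed in all patients who received any study drug, with no scan requirement. Use the Section 8.4 wording of the safety set (at least one dose of either drug), because Section 3.5 defines evaluable for safety by at least one combination dose. Report the EE versions only as supportive summaries, labelled as conditional on an on-treatment scan.

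Reconcile the EE definitions in Sections 3.5 and 8.4 on whether the scan must follow the protocol schedule.

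Keep the time origins of Section 8.12.2.3. Moving the OS start to first dose is a separate choice and is not needed to correct the population.

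The cost is a few sentences and one additional set of summaries. No new data are needed, since survival status is already collected without a scan condition. The downside is that reported survival becomes slightly less favourable.
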